1.0 INTRODUCTION

1.1 Rationale for Hypofractionation

Radiation therapy has a long and established role in the curative treatment of organ-confined prostate cancer[1]. However, the optimal radiation dose and treatment schedule remain unknown[2]. Typically, patients treated with external beam radiation therapy [EBRT] receive daily treatment five days per week for a total duration of 7-8 weeks[3]. More recently, published non-randomized and randomized data strongly suggests that radiation doses in the range of 78-81 Gy result in an improvement in five year biochemical freedom from relapse, even in “low risk (for regional/distant metastasis) patients [4] [5]. Delivery of these doses via highly conformal radiation techniques (including conformal proton beams) has been associated with minimal and acceptable significant acute and late treatment-related morbidity. At LLUMC, our current institutional standard for early-stage disease is to treat the prostate and immediately adjacent paraprostatic tissues with conformal proton beams alone to a radiation dose of ~81 CGE [Cobalt-Gray Equivalent, in which 1 proton Gy is assumed to equal 1.1 photon Gy], delivered over a period of nine weeks. This prolonged course, although well tolerated, can lead to logistical difficulties in terms of requiring patients (many of whom reside outside of the immediate area) to remain at LLU for periods of up to three months; this can serve as an absolute treatment barrier to some patients who would otherwise be candidates for conformal proton beam therapy but who are unable to remain at LLU for such a prolonged treatment course. A reduction in treatment time could therefore allow more patients to take advantage of this treatment modality that is currently possible.

Radiation induced mammalian cell death (including human cells) is classically described according to the linear-quadratic equation. Per this formula, the survival rate of a given cell will depend upon multiple factors including the overall radiation dose, the dose per treatment fraction, and the overall treatment time. The dose-response of tumors and normal tissue to fractionated radiotherapy can be described according to the alpha-beta ratio. This ratio is a parameter which numerically describes the fractionation sensitivity of a particular cell type. For example, the α/β ratio is typically high (≥ 10 Gy) for early-responding normal tissues (skin, mucosa) and most tumors, and low (< 5 Gy) for late-responding normal tissues (spinal cord, brain, bone). An obvious implication of the difference in α/β ratios between tumor and normal tissue is that it may therefore be possible to increase the “therapeutic ratio” by employing unconventional fractionation schedules.

Over the last 5-10 years there have been several published reports suggesting that the α/β ratio for prostate cancer cells is very low and is in fact lower than that for some of the surrounding adjacent normal tissues (bladder, rectum) [6] [7]. Although the absolute number varies, most publications suggest that the α/β ratio is between 1 and 3 [8] [9]. Should this be true, then treatment with hypofractionated regimens (shorter overall treatment time, larger treatment fractions) may prove to be more effective

than conventional fractionation. As will be mentioned below, this hypothesis has already been successfully tested in conformal proton beam treatment of numerous malignancies. This protocol is designed to investigate the safety and efficacy of conformal proton beam therapy of early stage prostate cancer in which treatment is administered via a hypofractionated regimen designed to be biologically equivalent to our current conventional fractionation schemata.

1.2 Hypofractionated Conformal Proton Beam Therapy of other tumors

The use of hypofractionation has a long and generally successful history in conformal proton beam therapy. Its use has been predicated by both the superior physical characteristics of protons as compared to x-rays (i.e., low entrance dose, sharply defined high dose area, lack of exit dose) and, until recently, the limited number of proton beam treatment centers in existence. Hypofractionated conformal proton beam therapy is routinely employed in the treatment of intra-ocular tumors, intra-cranial tumors (both benign and malignant), lung cancer, and early breast cancer. It is, therefore, reasonable to assume that an analogous level of success can be achieved in treatment of organ-confined prostate cancer, and this hypothesis is worthy of testing in a Phase I-II clinical trial.

1.3 Calculation of Biologically Equivalent Dose [BED]

In order to facilitate a comparison between our current institutional standard (81 CGE/45 Fractions) and the fractionation schedule to be employed in this protocol (60 CGE/20 Fractions) biologically equivalent doses [BED] will be calculated and the isoeffect model using the linear-quadratic equation will be used. Also, for the purposes of calculating the BED and isoeffective doses in this protocol two underlying assumptions will be made 1) complete repair of radiation-induced DNA injury between fractions and 2) there is no time factor. The calculated BED depends on the assumed α/β ratio, which in this protocol will be assumed to be 1.5 for tumor, 4.0 for rectum (a late responding tissue), and 10 for early responding tissues. The assumed α/β ratio used in each calculation will be indicated by a subscript e.g., BED_{1.5} indicates that the BED reported was calculated using an α/β of 1.5. The calculated BED's for the hypofractionated treatment and our current institutional protocol are as follows:

	BED_{1.5}	BED_{4.0}	BED_{10.0}
Conv	178	117	96
Hypofx	180	105	78

1.4 Phase I-II Trials of Hypofractionation Regimens in Prostate Cancer

Several reports detailing the efficacy and safety of hypofractionated conformal radiation therapy (with x-rays) of prostate cancer can be found in the literature. In the United States, Kupelian et al have recently reported five year bNED survival and morbidity in a group of patients treated with hypofractionated radiotherapy delivered via an IMRT approach [10]. One hundred patients with organ-confined prostate cancer were treated to 70 Gy delivered in 28 fractions (2.5 Gy/fx). Patients were treated in 1998, and the median follow up was 66 months. Androgen deprivation therapy was administered to 51% of the patients, with the duration of ADT limited to no more than six months. The PTV-CTV margin was 4mm posteriorally and 5-8 mm elsewhere. Freedom from biochemical failure was reported using both the ASTRO Consensus definition [11] and the RTOG Phoenix definition (nadir + 2 ng/ml). Results were reported according to prognostic groups, and the RTOG morbidity scoring system was used to report GI and GU morbidity.

The estimated rate of FFBR at five years post-treatment was 85% according to the ASTRO definition and 88% per the Phoenix definition. These biochemical results were similar to a group of contemporaneously treated patients who were treated with 3-D CRT to 78 Gy/39 fx. In the hypofractionated patients the combined rate of Grade 2-3 rectal morbidity was 11% at five years; again, this compares favorably to patients treated in a conventional manner to 78-80 Gy.

LLUMC has treated sixty-two patients with low-risk prostate cancer on a Phase I-II hypofractionation trial, in which they received 60 Gy/20 fractions. With a minimum follow-up of one year, to date there have been no Grade ≥ 3 complications, and the rate of Grade 2 GI/GU morbidity is 1.6%. These toxicity numbers compare favorably with those from our randomized dose-escalation trial and strongly suggest that further dose-escalation via hypofractionated techniques is medically feasible.

1.5 Randomized Trials of Hypofractionation

To date, the preliminary results from two randomized trials have been published. The Australian Trial compared 64 Gy/32 fx to 55 Gy/20 fx in men with favorable risk stage T1-T2 prostate cancer [12]. The primary trial endpoint was morbidity, and the total sample size of 220 patients (110 per arm) was powered to determine a difference in the frequency of mild late radiation morbidity of 20% with 90% power. Efficacy was considered to be a secondary endpoint. An interim analysis included the first 120 consecutively treated men. Median follow up was 43 months (range 23-62 months). Two dimensional EBRT was employed in each arm; no 3-D or IMRT was used or allowed. Morbidity was measured with the LENT-SOMA questionnaires. The GI component of this questionnaire emphasizes six symptoms (stool frequency, stool consistency, rectal pain, mucus discharge, tenesmus, and rectal bleeding). GU morbidity measures four symptoms (urinary frequency, urgency, dysuria, and

hematuria). Treatment efficacy was assessed both clinically and biochemically; the latter utilized PSA nadir and three consecutive rises as indications of biochemical relapse.

Of the ten symptoms measured only the prevalence of rectal bleeding at two years was different between the two arms, with bleeding reported in 42% of the hypofractionated patients vs. 24% in the conventionally treated arm ($p < 0.05$). The prevalence of late rectal bleeding in the conventionally treated arm is higher than expected and is most likely due to the two-dimensional methods employed. If one only considers those patients experiencing moderate to severe bleeding there is no difference between the arms (20 vs. 14%, $P < 0.05$). In terms of efficacy, there was no difference in the nadir PSA and the PSA levels 2 years following treatment between the arms. Using the ASTRO definition the 4-year estimated freedom from biochemical failure was 85.5% in the conventionally treated arm (BED_{10} 76.8, $BED_{1.5}$ 149.3) and 86.2% in the hypofractionated arm (BED_{10} 70.1, $BED_{1.5}$ 155.8).

Preliminary results of a Canadian randomized trial have also been recently published [13]. This trial compares 66 Gy/33 fx (standard arm) to 52.5 Gy/20 fx (hypofractionated arm) in patients with low and intermediate risk prostate cancer. Dose was prescribed to isocenter and the CTV-PTV margin was 15 mm, except, 10 mm posterioraly (at investigators discretion). Patients were treated via a four-field arrangement and although CT data was used for treatment planning in most patients, IMRT was not performed. It must be noted that the two arms were not designed to be isoeffective and that the biologically equivalent dose of the short arm is considerably less than the long arm (BED_{10} 66.3 vs. 79.2, $BED_{1.5}$ of 144 vs. 154). It is therefore not surprising that the five year failure rate (biochemical or clinical) is higher in the hypofractionated arm (59.95% vs. 52.95%, $P < 0.05$). At a median follow up of 5.7 years there is no difference in five year actuarial rate of grade 3+ GI/GU toxicity between the two arms.

1.6 Trial Justification

As has been previously described, hypofractionated conformal proton beam radiation therapy has become our institutional routine for the treatment of numerous solid tumors. Conformal proton beams, by virtue of their physical characteristics, permit a degree of normal tissue sparing that is simply not possible with x-rays [14]. In the treatment of prostate cancer, this difference is almost exclusively in the volume of normal tissue which receives a low to moderate radiation dose. This difference may and probably does have a profound impact in late normal tissue morbidity as radiation-induced late effects are moderated by many factors including total dose, dose per fraction, and volume of organ receiving any radiation dose. Given the degree of normal tissue sparing possible with protons, it is reasonable to assume that results achieved with x-ray therapy can be duplicated and quite possibly exceeded (in terms of reducing late effects) by treating in a similar fashion with conformal proton beams. Since ample support exists in the medical literature regarding the safety and apparent

efficacy of hypofractionated prostate cancer treatment via x-rays, it is reasonable and desirable to pursue an identical strategy with protons.

1.7 Patient Selection

This trial will be restricted to patients with low-risk prostate cancer, defined as Stages T1-2C, and Gleason Score 2-6 and PSA < 10. In this patient population the risk of seminal vesicle and lymph involvement is low enough (< 10%) to permit excluding these structures from the treatment volume.

1.8 Dose Selection

The hypofractionated dose of 60 CGE/20 Fx has been chosen because, as per the linear-quadratic equation (and assuming a BED of 1.5 for prostate cancer cells) it should be isoeffective in terms of biochemical DFS with our current institutional standard of 81 CGE/ 45 fractions [4]. In addition, the hypofractionated dose is similar to that which has been reported by Kupelian et al.

2.0 Objectives

2.1 Primary Objective

To determine if hypofractionated conformal proton beam radiation therapy of prostate cancer can result in late RTOG \geq Grade 3 treatment-related morbidity which is no worse than that engendered by our current institutional standard with conventional fractionation (81 CGE/45 fx). In PROG 9509, late Gr 2 and Gr3+ GI toxicity was 17 & 1 % respectively, Gr2 & Gr3+ GU toxicity was 20 & 3%.

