12.2. Sample Size

12.2.1. Sample Size

12.2.1.1. Phase I Component: Between 1990 and 2007, we have treated 4260 patients with early stage prostate cancer (clinical stage T1 or T2, initial PSA <10 ng/ml, KPS 90 or 100) with protons only. The 3-year actuarial rectal/urinary grade 3 toxicity rate was $0.69\% \pm 0.15\%$ SE in this cohort. We will conservatively assume the standard toxicity rate p_0 to be 1% and set the unacceptable toxicity rate p_1 at 5%. Statistical error rates will be set at $\alpha=10\%$ for a false positive result (calling the treatment too toxic when it is not) and $\beta=10\%$ for a false negative result (accepting that the treatment is not too toxic when in reality it is) when using a one-sided test of significance. The sample size meeting these requirements is 105 patients.

12.2.1.2. Phase II Component: In the same patient cohort, the 3-year actuarial rate of biochemical progression free survival (bPFS) was 96%. We will conservatively assume the standard 3-year biochemical failure rate p_0 to be 5% and set the unacceptable failure rate p_1 at 10%. Statistical error rates for false positive and false negative results will again be set at 10%. The required sample size is 187 patients, which exceeds the required sample size for the toxicity endpoint. An additional 35% will be added to this number to guard against ineligible or evaluable cases, resulting in 288 patients. In order to be conservative the sample size for the Phase I/II study will be set to 300 patients.

12.2.1.3. Assuming we accrue the target goal of 187 evaluable patients, a 5% late toxicity rate equates to 9.34 patients with toxicity. If we have 9 or fewer patients with toxicity, the protocol therapy will be considered for further study. In addition, we must also meet the goals for tumor control. Assuming the target goal of 187 patients, tumor control will be considered acceptable if 12 or fewer patients have biochemical failure within the first three years. For the protocol therapy to be recommended for further study, both the toxicity and tumor control outcomes must be considered acceptable. This equates to 9 or fewer patients with late toxicity, and 12 or fewer patients with recurrence. If the study accrues more or less than 187 evaluable patients, these cut-off numbers will be adjusted accordingly.

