With a sample size of 187 patients and an assumed late toxicity rate of 2%, we have an upper = 95% confidence limit of 5% for (grade ≥ 3) late toxicity. This upper bound corresponds to the limit we would accept in terms of toxicity.

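### The primary objective promises late toxicity no worse than the institutional standard, but a pass at 9 or fewer of 187 supports neither that claim nor the exclusion of a 5% rate

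*Combined protocol and SAP*

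**What the plan says.** Section 2.1 sets the primary objective as late RTOG grade 3 or higher "treatment-related morbidity which is no worse than that engendered by our current institutional standard with conventional fractionation", the standard being 81 CGE in 45 fractions. It states no margin. The next sentence gives the only numbers in that section, from PROG 9509: "late Gr 2 and Gr3+ GI toxicity was 17 & 1 % respectively, Gr2 & Gr3+ GU toxicity was 20 & 3" (per cent).

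Section 12.2.1.1 starts elsewhere. It describes 4,260 early-stage patients treated at the institution with protons only between 1990 and 2007, with a 3-year actuarial rectal/urinary grade 3 rate of 0.69% (SE 0.15%). It continues: "We will conservatively assume the standard toxicity rate p_0 to be 1% and set the unacceptable toxicity rate p_1 at 5" (per cent). Both error rates are 10%, one-sided. Beta is the chance of accepting the treatment when it is in fact too toxic. The toxicity sample size is 105.

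Section 12.2.1.3 takes the 187 evaluable patients required for the biochemical endpoint, multiplies by 5%, and lets the therapy go forward for further study on toxicity if 9 or fewer patients have late toxicity. Tumor control must also be acceptable. The closing paragraph of Section 12.2 says that an assumed 2% rate in 187 patients has an upper 95% limit of 5%, and adds: "This upper bound corresponds to the limit we would accept in terms of toxicity".

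**The concern.** The objective and the decision rule answer different questions. The objective, read as written, compares the new schedule with the institutional standard. The rule compares an observed count with 5%, a rate well above any version of that standard in the protocol. Nothing links 5% to the words of the objective, and the margin is absent from the section where the claim is made.

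The reference is also unsettled. Section 2.1 shows only PROG 9509; Section 12.2 uses only the institutional cohort. PROG gives GI and GU separately. Combined, they come to between 3% (complete overlap) and 4% (no overlap); the protocol does not give the overlap, so this range is an assumption. An observed rate of 3% to 4% could then be described as in line with PROG, or as roughly four to six times the institutional cohort (3/0.69 = 4.3; 4/0.69 = 5.8).

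At stake is what the trial may conclude about severe late toxicity, its primary endpoint.

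**Working it through.** **Inputs.** From Section 12.2: p0 = 1%, p1 = 5%, alpha = beta = 10% one-sided, n = 105 for toxicity, 187 evaluable patients, pass at 9 or fewer, cohort rate 0.69%. From Section 2.1: PROG grade 3+ GI 1% and GU 3%.

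**The plan's own figure.** Take the smallest n with a cut-off c such that P(X > c | 1%) ≤ 0.10 and P(X ≤ c | 5%) ≤ 0.10, X binomial. This gives n = 105 with c = 2: errors of 8.9% and 9.9%. The stated 105 reproduces.

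**How far 5% lies from each reference.**
- Observed cohort rate: 5/0.69 = 7.2.
- The design's p0: 5/1 = 5.
- PROG, assumed 4% to 3%: 5/4 = 1.25 to 5/3 = 1.7.

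**Chance of passing on toxicity**, P(X ≤ c) with X ~ Binomial(187, true rate):

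| True rate | c = 9 (stated) | c = 5 |
|---|---|---|
| 0.69% | >99.9% | 99.8% |
| 1% | >99.9% | 98.8% |
| 2% | 99.5% | 82.6% |
| 3% | 94.3% | 50.9% |
| 4% | 78.2% | 23.8% |
| 5% | 54.0% | 9.0% |

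A true 2% is 2/0.69 = 2.9 times the cohort rate and twice p0, and it almost always passes.

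**What particular results would show** (Clopper-Pearson limits).
- 9/187 = 4.8%: one-sided 95% lower limit 2.5%, upper limit 8.2%; one-sided 90% upper limit 7.5%. A just-passing result is significantly above both 0.69% and 1%, and does not exclude 5%.
- 6/187: one-sided 90% upper limit 5.6%. So passes with 6 to 9 events do not exclude 5% even at the 90% level.
- 5/187: one-sided 90% upper limit 4.9%.
- 4/187: one-sided 95% upper limit 4.8%. The closing paragraph's 2% rate is 0.02 × 187 = 3.74 patients, so its 5% upper limit corresponds to about 4 events, not 9.
- 0/187: one-sided 95% upper limit 1.6%. Even no events at all would not exclude rates above 0.69% or 1%.

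**Why the cut-off misses its error.** The rule takes the expected count under the unacceptable rate, 0.05 × 187 = 9.35, and rounds down. A cut-off near the expected count is met about half the time. With 187 patients, c = 6 accepts a true 5% in 17.0% and c = 5 in 9.0%, so 5 is the largest cut-off that keeps the stated 10%. It wrongly rejects a true 1% in 100 − 98.8 = 1.2%.

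**The stricter cut-off does not rescue the objective's wording.** With c = 5 a true 2% still passes 82.6% of the time.

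**The case against.** The strongest reply is that 5% is disclosed as the acceptable limit, that non-inferiority within a margin is ordinary usage, and that a pass leads only to further study. Much of this stands. The choice of 5% is not faulted here, and the sample size is right. But a non-inferiority claim needs its margin where the claim is made, and under the present cut-off a pass does not establish even that margin.

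It can also be said that the test does involve p0 = 1%. It does, but only as the null for calling the treatment too toxic. Not rejecting 1% is no evidence that the rate is 1%.

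Several stronger readings are tempting, and the documents do not support them:
- That a pass will be reported as no worse than the standard. Section 12.2.1.3 does not say so, and Sections 12.5.2 and 12.5.3 promise only observed results.
- That the PROG and cohort figures contradict each other. PROG is grade 3+, by organ, with no time point, and Section 2.2.1 shows that it included intermediate- and high-risk patients. The cohort figure is grade 3, rectal/urinary combined, 3-year actuarial. They are unreconciled, not shown to conflict.
- That sevenfold is the single correct multiple. It holds against the observed 0.69%; against the design's own p0 it is fivefold.
- That the present rule at least shows the rate to be below 5%. It does not.

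**Conclusion.** The concern holds as a mismatch between the objective, its reference and the decision rule. A pass at 9 or fewer of 187 cannot support the objective as worded: true rates of 2% and 3% pass 99.5% and 94.3% of the time, and the least favourable passing result lies significantly above the standard. Nor does a pass exclude 5%, which is accepted 54% of the time against a stated 10%.

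These figures assume 187 evaluable patients, independent outcomes and a simple count of patients with late toxicity. Section 12.2.1.3 gives no time window for that count, whereas the cohort rate is 3-year actuarial. The pass probabilities concern toxicity alone; the further requirement on tumor control lowers the chance of an overall recommendation but does not change what the toxicity result can show. The conclusion does not depend on the assumed PROG overlap.

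**What to change.** 1. Reword Section 2.1 so that the objective is to rule out a late grade 3 or higher GI/GU rate of 5% or more, and state that margin there.
2. Align the statistical cut-off in Section 12.2.1.3 with the stated beta: 5 or fewer of 187 gives 9.0% acceptance at a true 5% and 1.2% false rejection at 1%. If 9 or fewer is kept, state its actual 54% acceptance at 5% and do not claim that 5% is excluded. The new wording in step 1 is sound only with one of these two.
3. Name the institutional cohort as the single comparator, after confirming that its grade definition, time point and dose schedule match Section 2.1. Section 12.2.1.1 reports grade 3, not grade 3 or higher, and does not tie the cohort to 81 CGE in 45 fractions. Label the PROG figures as context and give their follow-up time.
4. Report the 3-year rate with its confidence interval beside 0.69%.

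The cost is text in Sections 2.1 and 12.2, a less favourable claim and, if adopted, a stricter cut-off: a true 2% rate would then pass 82.6% of the time instead of 99.5%. p0, p1 and the sample size are unchanged.
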